5.9 Clinical Criteria for Early Trial Termination

Early trial termination will be the result of the criteria specified below:

1. Quality or quantity of data recording is inaccurate or incomplete
2. Poor adherence to protocol and regulatory requirements
3. Incidence or severity of adverse drug reaction in this or other studies indicates a potential health hazard to subjects
4. Plans to modify or discontinue the development of the study drug

In the event of Merck decision to no longer supply study drug, ample notification will be provided so that appropriate adjustments to subject treatment can be made.

This document is confidential and the property of the University of Pennsylvania. No part of it may be transmitted, reproduced, published, or used by other persons without prior written authorization from the regulatory sponsor.

6.0 TRIAL FLOW CHART

6.1 Study Flow Chart

Trial Period:	Screening	Treatment cycles and week #									End of Treatment		
		C1				C2			C3 to C8	C9 onwards	Discon	Safety Follow-up Visit	Follow-up
Treatment Cycle^^:	-28 to -1	D0 (W0)	D3	D7	D14	D0	D7	D14	D0	D0			
Scheduling Window (Days):		-3 ^B	±1	±3	±3	±3	±3	±3	±3	±7	At time of Discon	30 days post discon	±2 weeks
Informed Consent	x												
Inclusion/Exclusion Criteria	x												
Demographics and Medical History	x												
Prior and Concomitant Medication Review	x	x				x			x	x	x		
Trial Treatment Administration		x				x			x	x			
Post-study anticancer therapy status											x	x	x
Survival Status											x	x	
Review Adverse Events		x				x			x	x	x	x	
Full Physical Examination	x	x				x			x	x	x	x	

Version 12, October 21, 2018. UPCC 46415: Phase I/II study of pembrolizumab in patients failing to respond to or relapsing after anti-CD19 chimeric antigen receptor modified T cell therapy for relapsed or refractory CD19+ lymphomas

This document is confidential and the property of the University of Pennsylvania. No part of it may be transmitted, reproduced, published, or used by other persons without prior written authorization from the regulatory sponsor.

Trial Period:	Screening	Treatment cycles and week #									End of Treatment		
Treatment Cycle^^:	Main Study Screening	C1				C2			C3 to C8	C9 onwards	Discon	Safety Follow-up Visit	Follow-up
Day (relative to each cycle):	-28 to -1	D0 (W0)	D3	D7	D14	D0	D7	D14	D0	D0			
Scheduling Window (Days):		-3 ^B	±1	±3	±3	±3	±3	±3	±3	±7	At time of Discon	30 days post discon	± 2 weeks
Vital Signs	x	x				x			x	x	x	x	
ECOG Performance Status (Appendix 12.1)	x	x				x			x	x	x	x	
Electrocardiogram (EKG)	x												
Pregnancy Test – Urine or Serum β-HCG	x	x ^B				x			x ^E	x		x	
PT/INR and aPTT	x												
CBC with Differential	x	x ^B	x ^C	x ^D	x ^D	x	x ^D	x ^D	x ^E	x		x	
Comprehensive Serum Chemistry Panel,, LDH	x	x ^B	x ^C	x ^D	x ^D	x	x ^D	x ^D	x ^E	x		x	
Uric acid, phosphate	x	x ^{BD}	x ^C	x ^D	x ^D	x	x ^D	x ^D	x ^I				
Urinalysis	x												
TSH with reflex to T4	x	x ^B				x			x	x ^F		x	
Tumor Imaging	x ^A	Week 12 then every 12 weeks from most recent imaging PET/CT, CT of chest/abdomen/pelvis, or MRI chest/abdomen/pelvis ± 2 wk for 24 months									x ^A		x ^A
HIV, Hep B sAg/sAb/cAb, HCV Ab	x ^G												

This document is confidential and the property of the University of Pennsylvania. No part of it may be transmitted, reproduced, published, or used by other persons without prior written authorization from the regulatory sponsor.

Trial Period:	Screening	Treatment cycles and week #									End of Treatment			
Treatment Cycle ^{^^} :	Main Study Screening	C1			C2			C3 to C8			C9 onwards	Discon	Safety Follow-up Visit	Follow-up
Day (relative to each cycle):	-28 to -1	D0 (W0)	D3	D7	D14	D0	D7	D14	D0	D0				
Scheduling Window (Days):		-3 ^B	±1	±3	±3	±3	±3	±3	±3	±7	At time of Discon	30 days post discon	± 2 weeks	
Archival or Newly Obtained Tissue Collection (optional)	x										x			
Correlative Studies Blood Collection ^H (optional)	x	x ^B	x ^H	x ^D	x ^D	x	x ^D	x ^D	through C4		x			

^{^^}Please note that for study purposes, Day 0 / Week 0 / Cycle 1 refers to the date of the first infusion

^A See Section 6.3

^BCycle 1, Day 0 labs will be drawn within 3 days prior to infusion; screening labs may double as Cycle 1, Day 0 labs if they are performed within this timeframe

^CLabs will be drawn Day 3 ± 1 day after Cycle 1 infusion

^DFor Cycles 1 and 2, labs will be drawn weekly ± 3 days at one week and two weeks after each infusion

^EFrom Cycle 3-8, labs will be drawn ± 3 days prior to each dose of pembrolizumab

This document is confidential and the property of the University of Pennsylvania. No part of it may be transmitted, reproduced, published, or used by other persons without prior written authorization from the regulatory sponsor.

^FBeginning with Cycle 9 of pembrolizumab), labs may be drawn every odd-numbered cycle (i.e. prior to every other dose) \pm 1 week until drug discontinuation.

^GWithin 3 months of enrollment

^HSee Section 6.5

^IOnly for Cycle 3

This document is confidential and the property of the University of Pennsylvania. No part of it may be transmitted, reproduced, published, or used by other persons without prior written authorization from the regulatory sponsor.

6.2 Physical examination and adverse events

Physical examination including vital signs, as well as determination of ECOG performance status will be obtained prior to start of each cycle of pembrolizumab.

Review of adverse events will be performed prior to start of each cycle of pembrolizumab.

Review of concomitant medications will be performed prior to the start of each cycle of pembrolizumab.

6.3 Imaging studies

^ABaseline imaging must be performed within 6 weeks of first dose of pembrolizumab. This may be obtained by contrast-enhanced CT, contrast-enhanced MRI, or PET/CT. Imaging for response assessment should be performed at week 12 after first dose of pembrolizumab, and then should be performed every 12 weeks from most recent imaging PET/CT, CT of chest/abdomen/pelvis, or MRI chest/abdomen/pelvis \pm 2 weeks until 24 months after first dose of pembrolizumab. After 24 months, subjects who did not discontinue study due to progression of lymphoma or toxicity will transition to the follow-up period and be followed with imaging every 6 months \pm 2 weeks until 60 months after first dose of pembrolizumab.

Subjects will be reimaged at the time of pembrolizumab discontinuation \pm 2 weeks unless they are coming off study for toxicity, coming off study with recently documented complete response (within 8 weeks), or coming off study after $>$ 1 year of follow-up.

6.4 Laboratory studies

Screening tests (within 28 days prior to enrollment): CBC with differential, CMP, uric acid, phosphate, TSH with reflex to T4, PT/PTT, HIV (to be performed within 3 months of enrollment), Hepatitis B surface antibody / surface antigen, core antibody (to be performed within 3 months of enrollment), Hepatitis C antibody (to be performed within 3 months of enrollment) urinalysis, urine or serum pregnancy test if the subject is a woman whose last menstrual period was $<$ 18 months ago. EKG will also be obtained.

Cycle 1, Day 0 (labs within 3 days prior to infusion; screening labs may double as Cycle 1, Day 0 labs if they are performed within this timeframe): CBC with differential, CMP, LDH, uric acid, phosphate, TSH with reflex to T4, urine or serum pregnancy test if the subject is a woman whose last menstrual period was $<$ 18 months ago.

Cycle 1, day 3 \pm 1 day: CBC with differential, CMP, LDH, uric acid, phosphate

This document is confidential and the property of the University of Pennsylvania. No part of it may be transmitted, reproduced, published, or used by other persons without prior written authorization from the regulatory sponsor.

Cycle 1 (labs one week and two weeks after cycle 1 infusion \pm 3 days): CBC with differential, CMP, LDH, uric acid, phosphate

Cycle 2 (labs within 3 days prior to the infusion): CBC with differential, CMP, LDH, uric acid, phosphate, TSH with reflex to T4, urine or serum pregnancy test if the subject is a woman whose last menstrual period was $<$ 18 months ago.

Cycle 2 (labs one week and two weeks after cycle 2 infusion \pm 3 days): CBC with differential, CMP, LDH, uric acid, phosphate

Cycles 3-8 (labs every 3 weeks within 3 days prior to each cycle): CBC with differential, CMP, LDH, uric acid (only for cycle 3), phosphate (only for cycle 3), TSH with reflex to T4, urine or serum pregnancy test if the subject is a woman whose last menstrual period was $<$ 18 months ago.

Cycles 9-onwards, labs prior to every cycle of pembrolizumab within 1 week prior to each cycle: CBC with differential, CMP, LDH, urine or serum pregnancy test if the subject is a woman whose last menstrual period was $<$ 18 months ago.

Cycles 9-onwards (labs prior to each odd cycle of pembrolizumab within 1 week prior to each cycle): TSH with reflex to T4

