6. Female subject of childbearing potential should have a negative urine or serum pregnancy within 72 hours prior to receiving the first dose of study medication. If the urine test is positive or cannot be confirmed as negative, a serum pregnancy test will be required.
7. Female subjects of childbearing potential should be willing to use 2 methods of birth control or be surgically sterile, or abstain from heterosexual activity for the course of the study through 120 days after the last dose of study medication (Reference Section 5.5.2). Subjects of childbearing potential are those who have not been surgically sterilized or have not been free from menses for > 1 year.
8. Male subjects should agree to use an adequate method of contraception starting with the first dose of study therapy through 120 days after the last dose of study therapy.

This document is confidential and the property of the University of Pennsylvania. No part of it may be transmitted, reproduced, published, or used by other persons without prior written authorization from the regulatory sponsor.

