5.5.2 Contraception

Pembrolizumab may have adverse effects on a fetus in utero. Furthermore, it is not known if pembrolizumab has transient adverse effects on the composition of sperm. Non-pregnant, non-breast-feeding women may be enrolled if they are willing to use 2 methods of birth control or are considered highly unlikely to conceive. Highly unlikely to conceive is defined as 1) surgically sterilized, or 2) postmenopausal (a woman who is ≥ 45 years of age and has not had menses for greater than 1 year will be considered postmenopausal), or 3) not heterosexually active for the duration of the study. The two birth control methods can be either two barrier methods or a barrier method plus a hormonal method to prevent pregnancy. Subjects should start using birth control from study Visit 1 throughout the study period up to 120 days after the last dose of study therapy.

The following are considered adequate barrier methods of contraception: diaphragm, condom (by the partner), copper intrauterine device, sponge, or spermicide. Appropriate hormonal contraceptives will include any registered and marketed contraceptive agent that contains an estrogen and/or a progestational agent (including oral, subcutaneous, intrauterine, or intramuscular agents).

Subjects should be informed that taking the study medication may involve unknown risks to the fetus (unborn baby) if pregnancy were to occur during the study. In order to participate in the study they must adhere to the contraception requirement (described above) for the duration of the study and during the follow-up period defined in section 7.2.2-Reporting of Pregnancy and Lactation to the Sponsor and to Merck. If there is any question that a subject will not reliably comply with the requirements for contraception, that subject should not be entered into the study.

This document is confidential and the property of the University of Pennsylvania. No part of it may be transmitted, reproduced, published, or used by other persons without prior written authorization from the regulatory sponsor.

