5.5.3 Use in Pregnancy

If a subject inadvertently becomes pregnant while on treatment with pembrolizumab, the subject will immediately be removed from the study. The site will contact the subject at least monthly and document the subject's status until the pregnancy has been completed or terminated. The outcome of the pregnancy will be reported to the Sponsor and to Merck without delay and within 24 hours to the Sponsor and within 2 working days to Merck if the outcome is a serious adverse experience (e.g., death, abortion, congenital anomaly, or other disabling or life-threatening complication to the mother or newborn).

The study investigator will make every effort to obtain permission to follow the outcome of the pregnancy and report the condition of the fetus or newborn to the Sponsor. If a male subject impregnates his female partner the study personnel at the site must be informed immediately and the pregnancy reported to the Sponsor and to Merck and followed as described above and in Section 7.2.2.

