7.1.1.14 Laboratory Procedures/Assessments

Details regarding specific laboratory procedures/assessments to be performed in this trial are provided below in the table: Laboratory Safety Evaluations (Hematology, Chemistry and Urinalysis)

Laboratory tests for hematology, chemistry, urinalysis, and others are specified in Table 5.

This document is confidential and the property of the University of Pennsylvania. No part of it may be transmitted, reproduced, published, or used by other persons without prior written authorization from the regulatory sponsor.

Table 5 Laboratory Tests

Hematology	Chemistry	Urinalysis	Other
Hematocrit	Albumin	Blood	Serum β -human chorionic gonadotropin†
Hemoglobin	Alkaline phosphatase	Glucose	(β -hCG)†
Platelet count	Alanine aminotransferase (ALT)	Protein	PT (INR)
WBC (total and differential)	Aspartate aminotransferase (AST)		aPTT
Red Blood Cell Count	Lactate dehydrogenase (LDH)	Microscopic exam (If abnormal)	
Absolute Neutrophil Count		results are noted	Thyroxine (T4)
Absolute Lymphocyte Count		Urine pregnancy test †	Thyroid stimulating hormone (TSH)
	Uric Acid		
	Calcium		
	Chloride		Blood for correlative studies
	Glucose		
	Phosphorus		
	Potassium		
	Sodium		
	Total Bilirubin		
	Direct Bilirubin (If total bilirubin is elevated above the upper limit of normal)		
	Total protein		
	Blood Urea Nitrogen		
† Perform on women of childbearing potential only. If urine pregnancy results cannot be confirmed as negative, a serum pregnancy test will be required. ‡ If considered standard of care in your region.			

This document is confidential and the property of the University of Pennsylvania. No part of it may be transmitted, reproduced, published, or used by other persons without prior written authorization from the regulatory sponsor.

Laboratory tests for screening or entry into the Second Course Phase should be performed within 10 days prior to the first dose of treatment. Results must be reviewed by the investigator or qualified designee and found to be acceptable prior to each dose of trial treatment.

This document is confidential and the property of the University of Pennsylvania. No part of it may be transmitted, reproduced, published, or used by other persons without prior written authorization from the regulatory sponsor.

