7.1.3.2 Treatment Period

Subjects will receive pembrolizumab every 3 weeks for up to 18 cycles or 54 weeks, whichever is later.

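### Section 6.4 orders no pregnancy test for an unsterilised, heterosexually active woman under 45 once her amenorrhoea reaches 18 months, though 5.5.2 still requires two contraceptive methods; other sections conflict with 6.4.

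*Combined protocol and SAP*

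**What the plan says.** Section 6.4 lists five occasions for a pregnancy test: screening, Cycle 1 Day 0, Cycle 2, Cycles 3-8 and Cycles 9 onwards. All five carry the same condition, "urine or serum pregnancy test if the subject is a woman whose last menstrual period was" less than 18 months ago. Age, sterilisation and sexual activity play no part in it.

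Section 5.5.2 requires two contraceptive methods unless conception is highly unlikely: "Highly unlikely to conceive is defined as 1) surgically sterilized, or 2) postmenopausal", or not heterosexually active during the study. It defines the second of these with an age term: "a woman who is ≥ 45 years of age and has not had menses for greater than 1 year will be considered postmenopausal". The duty is a condition of taking part: "In order to participate in the study they must adhere to the contraception requirement".

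Three other places bear on testing:

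- Inclusion 7 (Section 5.1.2) has its own definition, without age: "Subjects of childbearing potential are those who have not been surgically sterilized or have not been free from menses for > 1 year". Inclusion 6 asks women of childbearing potential for a negative test within 72 hours before the first dose.
- The Table 5 footnote (Section 7.1.1.14) says "Perform on women of childbearing potential only".
- The flow chart in Section 6.1 marks a pregnancy test at screening, at every dosing visit and at safety follow-up, with no condition on last period, age or sex. Section 5.2.2 requires the flow-chart assessments to be completed before each dose.

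**The concern.** For contraception, the protocol regards an unsterilised, heterosexually active woman under 45 as able to conceive regardless of the length of her amenorrhoea. For testing under 6.4, it stops regarding her so at 18 months. Section 6.4 is the only text that sets a condition visit by visit, so it is a natural source for a site deciding whom to test.

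The stake is patient safety. Section 5.5.2 warns of possible harm to a fetus, and Section 5.5.3 states: "If a subject inadvertently becomes pregnant while on treatment with pembrolizumab, the subject will immediately be removed from the study". That safeguard works only if a pregnancy is detected. The contraception duty itself is intact, and nothing in Section 8 depends on the point.

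**Working it through.** **Rules side by side, for an unsterilised, heterosexually active woman under 45 with 18 or more months of amenorrhoea**

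| Text | Result for her |
|---|---|
| 5.5.2 | No exemption applies; two methods required |
| 6.4 | Condition false at all five entries; no test |
| Inclusion 7, literal *or* | Of childbearing potential, because not sterilised; inclusion 6 and Table 5 apply |
| Inclusion 7, if more than 1 year without menses is enough to exempt | Not of childbearing potential; inclusion 6 and Table 5 do not apply |
| 6.1 flow-chart row | Test at every dosing visit and at safety follow-up |

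For some other women 6.4 is stricter than 5.5.2. It tests women of 45 or over with between 12 and 18 months of amenorrhoea, and sterilised women who still menstruate. The shortfall is confined to the group above.

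**Pre-dose tests ordered by 6.4 alone**

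The plan gives no figure of its own to reproduce. Inputs:

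- Schedule, from Section 7.1.3.2: "Subjects will receive pembrolizumab every 3 weeks for up to 18 cycles or 54 weeks, whichever is later". Taking 18 doses on time, dose k falls at week 3(k-1), so dose 18 is at week 51.
- Threshold, from 6.4: 18 months.
- Conversion: 365.25 / 12 / 7 = 4.348 weeks per month.
- A = months of amenorrhoea at first dose, assumed to continue throughout and judged on the dosing day.

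A test is ordered before dose k if A + 3(k-1)/4.348 < 18, that is, if k-1 < (18 - A) × 4.348 / 3.

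| A (months) | Limit on k-1 | Tests ordered, of 18 | Not ordered |
|---|---|---|---|
| 6 | 17.39 | 18 | 0 |
| 12 | 8.70 | 9 | 9 |
| 15 | 4.35 | 5 | 13 |
| 17 | 1.45 | 2 | 16 |
| 18 or more | 0 or below | 0 | 18 |

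Dose 18 comes 51 / 4.348 = 11.73 months after the first, so all 18 tests are ordered only if A < 18 - 11.73 = 6.27 months. A woman who enters at 12 months is tested before doses 1-9 and, under 6.4, not before doses 10-18.

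These counts describe 6.4 and nothing else. On the literal reading of inclusion 7, inclusion 6 adds a baseline test. If Table 5 and the flow-chart row are then applied together, tests could be due before all 18 doses.

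**The case against.** The strongest reply is that the rest of the protocol does schedule a test for her. Section 5.2.2 makes the flow chart a precondition for dosing, Section 7.1.3 takes visit requirements from it, and its pregnancy-test row has no 18-month limit. Section 7.1 says the flow chart, Section 6.0, summarises the procedures; it does not say that the chart yields to 6.4, which is itself part of Section 6. Table 5, offered as the detailed laboratory text, covers her if inclusion 7 is read literally. Section 7.1 also lets the investigator, the Sponsor or Merck require additional tests.

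Most of that stands, and it rules out a stronger reading. From 6.4 a reader might infer that such a woman would go through the whole trial untested. The documents do not support that: a site working from the flow chart would test her at every dose.

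It does not remove the conflict. The flow-chart row states no condition at all, not even sex, so a site must look elsewhere to learn whom to test. Table 5 sets no visits and rests on a definition that reads two ways. The extra tests under Section 7.1 are discretionary. No text says which rule prevails.

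It can also be said that a testing trigger and a contraception exemption need not share a cut-off. That is fair in general, and 18 months is a longer period than the 1 year in 5.5.2. It does not explain why testing should lapse, on menstrual history alone, for a woman whom 5.5.2 declines to call postmenopausal.

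**Conclusion.** The point holds as an internal conflict, of minor severity. Section 6.4 switches off scheduled testing for a narrow group that 5.5.2 treats as fertile, while the flow chart, and on one reading inclusion 6 and Table 5, keep it on. Under 6.4 alone the pre-dose tests are 0, 5 or 9 of 18 for amenorrhoea of 18 or more, 15 or 12 months at first dose. This assumes 18 doses on schedule, continuing amenorrhoea, and no sterilisation or abstinence.

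The documents give no age or sex distribution, so the number affected is unknown; of 12 patients it may be few or none. Endpoints, power and error rates are untouched.

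**What to change.** 1. Keep the 18-month trigger and add to all five entries in 6.4: *or who is under 45 and not surgically sterilised, regardless of time since last period*.
2. Apply the same combined condition to the safety follow-up test, which the flow chart marks and 6.4 does not list.
3. Align inclusion 7 with 5.5.2: not of childbearing potential means surgically sterilised, or aged 45 or over with more than 1 year without menses. Refer to that definition in inclusion 6 and Table 5.
4. Delete *only* from the Table 5 footnote, so that it does not cancel tests that 6.4 orders outside that definition.

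Adding to the trigger is better than replacing it with the 5.5.2 definition. Replacement would remove 9 of 18 tests from a woman of 45 or over with just over 12 months of amenorrhoea at first dose (9 - 0), and 18 of 18 from a sterilised woman who still menstruates (18 - 0). The addition removes none of the tests in 6.4 and brings every case in the table to 18 of 18.

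The cost is amendment wording and, measured against 6.4 alone, at most 18 extra pre-dose tests, one at screening (which may double as the Cycle 1 test) and one at safety follow-up per affected woman, at visits that already draw blood. Abstinent women under 45 would also be tested, as 6.4 already does below 18 months. On the literal reading of inclusion 7, the new definition takes unsterilised women of 45 or over with 18 or more months of amenorrhoea out of inclusion 6 and its baseline test; 5.5.2 already calls them postmenopausal. Sample size and analysis are unchanged.
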